#### 5.8.4 Identity of Study Drugs

Interferon beta-1a (AVONEX) is indicated for the treatment of relapsing forms of multiple sclerosis (MS), to include clinically isolated syndrome, relapsing-remitting disease, and active secondary progressive disease, in adults. AVONEX is a 166 amino acid glycoprotein with a molecular weight of approximately 22,500 daltons. AVONEX is available for intramuscular injection as a lyophilized powder, single-use prefilled syringe, or a single-use prefilled autoinjector. A vial of AVONEX is a sterile, white to off-white lyophilized powder for intramuscular injection after reconstitution with supplied diluent (Sterile Water for Injection, USP). Each vial of reconstituted AVONEX contains 30 micrograms of interferon beta-1a; 15 mg Albumin (Human), USP; 5.8 mg Sodium Chloride, USP; 5.7 mg Dibasic Sodium Phosphate, USP; and 1.2 mg Monobasic Sodium Phosphate, USP, in 1.0 mL at a pH of approximately 7.3. A prefilled syringe of AVONEX is a sterile liquid for intramuscular injection. Each 0.5 mL (30 microgram dose) of AVONEX in a prefilled glass syringe contains 30 micrograms of interferon beta-1a, 0.79 mg Sodium Acetate Trihydrate, USP; 0.25 mg Glacial Acetic Acid, USP; 15.8 mg Arginine Hydrochloride, USP; and 0.025 mg Polysorbate 20 in Water for Injection, USP at a pH of approximately 4.8. AVONEX PEN is a sterile liquid for intramuscular injection in a prefilled glass syringe surrounded by an autoinjector. Each 0.5 mL (30 microgram dose) in the AVONEX PEN contains 30 micrograms of interferon beta-1a, 0.79 mg Sodium Acetate Trihydrate, USP; 0.25 mg Glacial Acetic Acid, USP; 15.8 mg Arginine Hydrochloride, USP; and 0.025 mg Polysorbate 20 in Water for Injection, USP at a pH of approximately 4.8.

Peginterferon beta-1a (PLEGRIDY) is an interferon beta indicated for the treatment of relapsing forms of multiple sclerosis (MS) to include clinically isolated syndrome,

relapsing-remitting disease, and active secondary progressive disease, in adults. PLEGRIDY (peginterferon beta-1a) is an interferon beta-1a to which a single, linear 20,000 dalton (Da) methoxy poly(ethyleneglycol)-O-2-methylpropionaldehyde molecule is covalently attached to the alpha amino group of the N-terminal amino acid residue. The molecular mass of PLEGRIDY is approximately 44,000 Da, consistent with the mass of the protein (approximately 20,000 Da), the carbohydrate moieties (approximately 2,500 Da), and the attached poly(ethylene glycol). However, because of the extended and flexible nature of the attached poly(ethylene glycol) chain, the apparent mass of PLEGRIDY in solution is greater than 300,000 Da. The more than 10-fold increase in apparent mass of PLEGRIDY compared to interferon beta-1a has been shown to contribute to the reduced clearance in vivo. PLEGRIDY is available as a single-dose prefilled pen or single-dose prefilled syringe. PLEGRIDY PEN is composed of an autoinjector that surrounds a prefilled glass syringe containing 0.5 mL of a sterile solution in water for injection of 63, 94, or 125 micrograms of peginterferon beta-1a, 15.8 mg of L-arginine HCl, 0.79 mg of sodium acetate trihydrate, 0.25 mg of glacial acetic acid, and 0.025 mg of polysorbate 20. The pH is approximately 4.8. A prefilled syringe of PLEGRIDY for subcutaneous injection contains 0.5 mL of a sterile solution in water for injection of 63, 94, or 125 micrograms of peginterferon beta-1a, 15.8 mg of L-arginine HCl, 0.79 mg of sodium acetate trihydrate, 0.25 mg of glacial acetic acid, and 0.025 mg of polysorbate 20. The pH is approximately 4.8.

Subjects administered placebo will received either a placebo intramuscular injection or placebo subcutaneous injection. A placebo intramuscular injection of equal volume and comparable pH to the diluent for high dose interferon beta-1a will be injected into upper arm intramuscularly for 6 subjects in the placebo treatment arm. A placebo subcutaneous injection of equal volume and comparable pH to the diluent for high dose peginterferon beta-1a will be injected into the upper arm subcutaneously for 6 subjects in the placebo treatment arm.

## **5.8.5 Management of Clinical Supplies**

### **5.8.5.1 Study Drug Packaging and Storage**

The active study drugs will be obtained from commercial sources. Storage instructions for the active study drugs are as follows:

- AVONEX in prefilled syringes should be stored in a 2°C to 8°C (36°F to 46°F) refrigerator. Once removed from the refrigerator, AVONEX in a prefilled syringe should be allowed to warm to room temperature (about 30 minutes). Do not use external heat sources such as hot water to warm AVONEX in a prefilled syringe. Should refrigeration be unavailable, AVONEX in a prefilled syringe can be stored at ≤ 25°C (77°F) for a period up to 7 days. Once the product is removed from the refrigerator, it must not be stored above 25°C (77°F). If the product has been

exposed to conditions other than those recommended, DISCARD THE PRODUCT and DO NOT USE. DO NOT EXPOSE TO HIGH TEMPERATURES. DO NOT FREEZE. Protect from light. Do not use beyond the expiration date stamped on the syringe.

- PLEGRIDY should be stored in the closed original carton to protect from light until ready for injection. Store in a refrigerator between 2°C to 8°C (36°F to 46°F). Do not freeze. Discard if frozen. Once removed from the refrigerator, PLEGRIDY should be allowed to warm to room temperature (about 30 minutes) prior to injection. Do not use external heat sources such as hot water to warm
- Placebo should be stored below 25 °C (77 °F). Do not freeze. Vials should be protected from the light until time of use.

### **5.8.5.2 Study Drug Accountability**

Good clinical documentation practices will be employed to record the receipt, storage conditions, accountability, and use or return of the study drug. The study drug will be stored in a secure location with access to the study personnel who will be managing the storage, dispensing, and accountability of the study drug.

Upon completion or termination of the study, final accountability review by the study monitor, and written authorization from the sponsor, all unused and/or partially used study drug should be returned or destroyed at the study clinic. It is the investigator's responsibility to ensure that the sponsor has provided written authorization for study drug disposal, the disposal process follows the study clinic's standard operating procedures, and appropriate records of the disposal are documented and maintained. No unused study drug may be disposed until fully accounted for by the study monitor (or designee). Documentation of unused study drug should include subject number, medication identity (medication #, period #), date, and quantity of study drug used.

### **5.8.6 Blinding**

The pharmacist (and designated staff member responsible for confirmation of study drug dose) will be unblinded to subject treatment assignment; however, the pharmacist will not perform any study procedures other than study drug preparation and dispensing.

Subjects and staff will be blinded to treatment assignment during confinement, but route of administration will not be blinded. The blind will be maintained through a randomization schedule held by the dispensing pharmacist. Subjects and staff will be informed of a subject's end of study day when discharged from confinement. Subjects and staff will not be informed of the specific treatment arm assignment. The clinical research nurse will administer the subcutaneous study drug in unit dose containers that are not transparent.

### **5.8.6.1 Breaking the Blind**

The study drug blind will not be broken by the investigator or designee unless information concerning the study drug is necessary for the medical treatment of the subject. For unblinding a subject, the randomization information for unblinding can be obtained by contacting the dispensing pharmacist. The sponsor or medical monitor must be notified immediately if the study drug blind is broken. The date, time, and reason that the blind was broken will be recorded in the source documents. If the blind is broken by the investigator or designee, the study drug must be stopped immediately, and the subject must be withdrawn from the study. Data or specimens already collected from subjects who discontinue prematurely and for whom the blind is broken will be made available for analysis if needed.

### **5.8.7 Treatment Compliance**

At Screening, as part of the inclusion criteria, it will be confirmed that subjects are able to comply with the protocol-defined procedure of injecting subcutaneous study drug. All doses of the study drug will be administered in the study clinic either under direct observation of or administered by clinic personnel and recorded in the eCRF. If a subject vomits after dosing, the event will be documented as an AE. The decision to replace any subject who vomits after dosing will be made as described in Section 5.5.2.

### **5.8.8 Prior and Concomitant Medications**

Subjects are prohibited from using any prescription or nonprescription drugs (including aspirin or nonsteroidal anti-inflammatory drugs (NSAIDs) and excluding oral contraceptives and acetaminophen) within 14 days or 5 half-lives (whichever is longer), or complementary and alternative medicines within 28 days before the first dose of study drug.

Subjects are also prohibited from currently participating in another clinical study of an investigational drug and may not have been treated with any investigational drug within 30 days or 5 half-lives (whichever is longer) of the compound.

Subjects must be instructed not to take any medications, including over-the-counter products, without first consulting with the investigator.

### **5.8.9 Subject Restrictions**

Subjects are not allowed to use nicotine-containing products (e.g., cigarettes, cigars, chewing tobacco, snuff) within 6 weeks before Screening. In addition, subjects are not allowed to ingest alcohol, xanthine-containing products (e.g., tea, coffee, chocolate, cola), caffeine, grapefruit, or grapefruit juice for 48 hours before dosing and throughout the study. Subjects are not allowed to use aspirin or NSAIDs within 14 days before the first

dose of study drug. Subjects will be asked if they have used any of these substances and their responses will be recorded on the eCRF.

Subjects must be able to tolerate a controlled, quiet study conduct environment, including avoidance of music, television, movies, games, and activities that may cause excitement, emotional tension, or arousal during prespecified times (e.g., before and during ECG extraction windows) throughout the duration of the study.

Subjects must be willing to comply with study rules, including the meal schedule, attempting to void at specified times (e.g., before ECG extraction windows), remaining quiet, awake, undistracted, motionless, and supine during specified times, and avoiding vigorous exercise as directed throughout the duration of the study. Subjects will not be allowed to sleep during any ECG extraction periods.

Standardized meals will be served at consistent times relative to dosing, and no food or fluids will be served containing caffeine. Outside of meal times, the subjects will only be allowed to intake water, which will be available ad libitum.

## **5.9. Statistical Methods**

### **5.9.1 Sample Size**

Up to 98 healthy subjects will be enrolled (including 14 potential replacement subjects). The sample size was determined empirically. Twelve subjects per arm was deemed adequate for the pharmacokinetic and pharmacodynamic assessments in this study.

### **5.9.2 Analysis Populations**

The PD and PK populations will include all subjects who receive study drug and have at least 1 estimable PD or PK parameter, respectively, after dosing.

### **5.9.3 General Statistical Considerations**

All data will be presented in data listings. Data from subjects excluded from an analysis population will be presented in the data listings but not included in the calculation of summary statistics. Demographic and baseline characteristics will be summarized overall and by treatment for all subjects.

### **5.9.4 Subject Disposition**

The number of subjects who enroll in the study and the number and percentage of subjects who complete each assessment will be presented. The frequency and percentage of subjects who withdraw or discontinue from the study and the reason for withdrawal or discontinuation will be summarized.

## 5.9.5 Demographics and Baseline Characteristics

Descriptive statistics will be used to summarize demographic and baseline subject characteristics. For continuous variables, the mean, median, standard deviation (SD), minimum, and maximum values will be reported. For categorical (nominal) variables, the number and percentage of subjects (or observations) will be reported.

## 5.9.6 Primary Analysis

### 5.9.6.1 Pharmacodynamic Analyses

#### Neopterin and MxA protein

AUEC will be calculated for each subject. For each dose, separate intervals will be used for the AUEC assessment to truncate noise introduced from baseline fluctuations. Maximum decrease from baseline will be determined from all sampled timepoints. For both assessments and biomarkers, measures will be log-transformed and utilize an ANCOVA approach for calculating geometric means and 90% confidence intervals for each treatment. PD parameters of Avonex or Plegridy will be listed and summarized using descriptive statistics (n, geometric mean, coefficient of variation, minimum, median, and maximum).

Separate population PD analyses will be conducted using nonlinear mixed effect modeling with NONMEM. AUECs calculated for each subject from all doses for a drug and placebo patient will be combined and evaluated assuming a saturating  $E_{max}$  relationship to characterize system parameters such as  $E_{max}$  and  $EC_{50}$ .

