**Primary Endpoint**

1. The values and variability of standard PD metrics (AUEC and maximal difference at a single time-point) for neopterin at low, intermediate, and high doses of interferon beta-1a and peginterferon beta-1a.

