**Primary PD Assessments:**

- Area under the effect curve (AUEC) change from baseline truncated after return to baseline
- Percentage area under the effect curve (pAUEC) change from baseline truncated after return to baseline
- Maximum change from baseline at single time-point

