### **4.2. Secondary Endpoints**

The secondary endpoints of this study are:

1. The values and variability of standard PD metrics (AUEC and maximal difference at a single time-point) for MxA at low, intermediate, and high doses of interferon beta-1a and peginterferon beta-1a.
2. The values and variability of pharmacokinetic characteristics ( $C_{max}$  and AUC of free drug concentration) at low, intermediate, and high doses of interferon beta-1a and peginterferon beta-1a.
3. Parameters ( $E_{max}$ , and  $EC_{50}$ ) calculated by the model after combining data from low, intermediate, and high doses of interferon beta-1a and peginterferon beta-1a with placebo data.

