## **5.7. Study Procedures**

### **5.7.1 Pharmacokinetic Assessments**

#### **5.7.1.1 Pharmacokinetic Sample Collection**

Pharmacokinetic blood samples (5 mL) will be collected at the following time points:

- Day 1: 0 (predose), 1, 3, 6, 8, 16, 24 h
- Day 2: 32, 40, 48 h
- Day 3, 4, 5, 6, 7, 8\*, 9\*, 10\*, 14\*

\*After Day 7 for peg-interferon beta-1a (Plegridy) only

Blood samples will be collected by direct venipuncture or by inserting an IV catheter into the subject's forearm region. Each blood sample will be labeled with subject number, study number, study day, time point, event, and a barcode that matches that belonging to the subject.

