### 5.8.2 Dose Selection

#### 5.8.2.1 Avonex

The high dose for beta-interferon is 30 µg, which is the clinical dose. The mid-dose is 15 µg and the low dose is 7.5 µg. The dose selection rationale is based on available data for the PK and PD dynamic range of beta-interferon. This dose range will cover the sensitive dose-area-under-the effect curve (AUEC) relationship and dose- $E_{max}$  (nadir) relationship of the PD response (neopterin). Doses within the study range and greater have been safely administered to healthy subjects.

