## Table of Abbreviation

Abbreviation	Definition
AUC 0-inf	area under the concentration-time curve from time zero to infinity
AUC 0-t	area under the concentration-time curve from time zero to last on-study sample
AUEC 0-t	area under the effect curve from time zero to last on-study sample
AUEC	area under the effect curve
pAUEC 0-t	percentage area under the effect curve from time zero to last on-study sample
CL/F	apparent clearance
C max	maximum observed concentration
EC 50	the exposure that gives-half maximal response, model parameter
ED 50	the dose that gives-half maximal response, model parameter
E max,exp	maximum PD response, model parameter – concentration analysis
E max,dose	maximum PD response, model parameter – dose analysis
FDA	Food and Drug Administration
IFN β-1a	interferon beta-1a (Avonex®)
K el	elimination rate
mg	milligram
ΔMxA dec, max	maximum increase from baseline in MxA protein
ΔNeopterin dec, max	maximum increase from baseline in neopterin
PD	pharmacodynamic
pegIFN β-1a	pegylated interferon beta-1a (Plegridy®)
PK	pharmacokinetic
RNA	ribonucleic acid
SC	subcutaneously
SD	standard deviation
T max	time of maximum concentration (C max )
t 1/2	terminal half-life
V/F	apparent volume of distribution

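### The protocol's analysis text takes the single-timepoint PD metric as a maximum decrease from baseline, the SAP takes it as a maximum increase, and neither document acknowledges the reversal

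*Protocol*

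**What the plan says.** Protocol 5.9.6.1, repeated in the synopsis under Primary Analysis, covers neopterin and MxA together: "Maximum decrease from baseline will be determined from all sampled timepoints". It continues: "For both assessments and biomarkers, measures will be log-transformed", with ANCOVA, geometric means and 90% confidence intervals for each treatment. The dose rationales in 5.8.2.1 and 5.8.2.2 use the same downward language, with the wording "nadir) relationship of the PD response (neopterin".

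The protocol's endpoint and parameter lists give no direction. Section 4.1 and the synopsis have "maximal difference at a single time-point" as one of the two primary neopterin metrics, and 4.2 repeats it "for MxA at low, intermediate, and high doses of interferon beta-1a and peginterferon beta-1a". The synopsis PD assessments and 5.7.2.3.1 have "Maximum change from baseline at single time-point".

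The SAP goes the other way. Its abbreviation table defines the neopterin symbol as "maximum increase from baseline in neopterin". Sections 4.1, 4.2, 7.3.1 and 7.3.2 use the increase for neopterin and MxA, summarised by arithmetic mean, SD and CV. The symbols nevertheless carry the subscript dec, max, and 4.2 names an undefined Neopterin-Cmin as an exposure-response variable where 7.5 models the maximum increase. The version 2 change log records the switch from geometric mean to mean, because changes from baseline can be negative in placebo and at low doses.

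**The concern.** The trial exists to report the values and variability of these metrics, so that future similarity studies can be designed from them. A maximum decrease and a maximum increase from the same profile are different quantities. For a rising marker, the largest fall below baseline depends mainly on how high the single pre-dose value happened to be and on scatter in the samples near baseline. It carries little information about the drug. The log step then removes every subject whose samples all lie above the pre-dose value, because the change is not positive.

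Anyone who programmes from Protocol 5.9.6.1, or checks the report against it, meets a stated rule for part of the primary endpoint that the SAP contradicts. No section of either document says which one prevails.

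**Working it through.** **Side by side**

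| Item | Protocol 5.9.6.1 and synopsis | SAP 4.1, 4.2, 7.3.1, 7.3.2 | Difference explained? |
|---|---|---|---|
| Direction | maximum decrease | maximum increase | no |
| Summary scale | log, geometric mean | arithmetic mean, SD, CV | yes, SAP change log |
| Model and interval | ANCOVA, 90% CI | none | no |

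No sample-size or power figure depends on this metric, so there is no plan figure to reproduce.

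**Sample counts.** SAP Attachment A lists 5 post-dose samples on Day 1, 3 on Day 2 and 5 on Days 3-7: 5 + 3 + 5 = 13. Days 8, 9, 10 and 14 in arms D-G make 17. Protocol 5.7.1.1 lists 6 + 3 + 5 = 14, or 18 with the four later days. It falls to 13 and 17 only if the 48 h and Day 3 samples are one draw, which the protocol does not say. The later days carry the note "After Day 7 for peg-interferon beta-1a (Plegridy) only", so as listed placebo has 14 under the protocol and 17 under the SAP. SAP 6.1 takes one pre-dose sample (Day 1, time 0) as baseline.

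**No response.** With exchangeable errors, the pre-dose value is the lowest (or the highest) of k + 1 values with probability 1/(k + 1). The chance of at least one such subject among 12 is 1 - (k/(k + 1))^12.

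| k | Log undefined, per subject | At least one of 12 |
|---|---|---|
| 13 (SAP, A-C) | 1/14 = 7.1% | 59% |
| 14 (protocol as listed) | 1/15 = 6.7% | 56% |
| 17 (SAP, D-G) | 1/18 = 5.6% | 50% |
| 18 (protocol as listed) | 1/19 = 5.3% | 48% |

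These hold equally for a decrease and an increase. They count against logging a change, not against either direction.

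**Response upward (illustration).** None of the following inputs is in the documents:
- Within-subject CV of 10% or 20%, as independent log-normal error on every sample including the pre-dose one.
- True profile 1 + rise x shape(t), with every shape equal to 0 at time 0.
- Six shapes: (t/p)^m exp(m(1 - t/p)) with p = 24 or 40 h and m = 2 or 4, and two biexponentials with rates 0.1/0.02 and 0.05/0.03 per h. The same shapes serve both products.
- 100,000 simulated subjects per cell. Times are read from SAP Attachment A with Day 3 = 48 h. For the protocol listing, Day 3 = 72 h.

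Share of subjects with maximum decrease at or below 0 (range over shapes and CVs):

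| Peak rise | A-C, SAP | D-F, SAP | A-C, protocol listing |
|---|---|---|---|
| 33% | 11-31% | 7-16% | 10-26% |
| 50% | 12-41% | 8-19% | 11-33% |
| 67% | 13-49% | 8-21% | 11-40% |
| 100% | 13-62% | 9-25% | 12-51% |

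Repeat runs agree to within about two percentage points, hence the overall SAP-schedule ranges of about 11-63% and 7-26%. The log of the maximum increase is undefined in at most about 2% of subjects. From the lowest shares, the chance of at least one undefined decrease among 12 is 1 - (1 - 0.106)^12 = 74% in A-C and 1 - (1 - 0.074)^12 = 60% in D-F on the SAP schedule. It is about 71% in A-C on the protocol listing.

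At CV 10% on the SAP schedule, as the true rise goes from 0 to 100%, the mean maximum increase goes from 18-19% of baseline to 106-116%. The mean maximum decrease goes from 16% to between -4% and 12% in A-C, and from 17% to 8-14% in D-F. The decrease does not track the response.

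**The case against.** The SAP is the document that sets out the analysis methods, and wherever it specifies an analysis it uses the increase. The protocol's formal endpoints and parameter list are direction-neutral and so agree with it. The conflict comes down to one sentence, repeated in the synopsis, and a parenthesis in the dose rationale that is not an analysis rule. All of this stands. It limits the consequence, but it does not remove the contradiction in the protocol's stated primary analysis.

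The direction-specific percentages rest on chosen CVs, rises and shapes, and they shift with the schedule: the top of the A-C range is about 51% on the protocol's listed times. That also stands. They show the kind of failure to expect and are not a property of this trial.

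Three stronger readings are tempting, and the documents do not support them:
- *The change of scale is also unreconciled.* The SAP change log states the switch from geometric to arithmetic mean and gives a sound reason. Only the direction, the ANCOVA and the 90% intervals go unexplained. The log's general remark that PD parameter text was updated for clarity does not cover them.
- *The Cmin entry creates a second exposure-response analysis.* SAP 7.5 models the maximum increase, so this is a wrong label.
- *The protocol's direction is shown to be wrong.* Neither document contains data that settle which way the marker moves. The protocol's rule fails on the SAP's own reading, which is as far as the text goes.

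**Conclusion.** The concern holds for direction and for the dropped ANCOVA and intervals. A stated rule for part of the primary endpoint, and for the matching MxA endpoint, is contradicted by the SAP without acknowledgement. If the marker rises and the protocol text is followed, the metric would be mostly noise. Under the assumptions above, its log would be undefined in roughly one subject in ten up to about six in ten in arms A-C, and about 7-26% in D-F, on the SAP schedule. If the SAP governs, the reported analysis is largely unaffected. A reader might infer that the trial's primary results are at risk. They are so only if Protocol 5.9.6.1 is applied literally. This should be corrected, but nothing in the design turns on it.

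**What to change.** - **Protocol 5.9.6.1 and synopsis:** replace the maximum decrease with the SAP's maximum increase from baseline, and remove the log and geometric-mean step for change-from-baseline PD metrics.
- **ANCOVA and 90% confidence intervals:** state whether they are kept, on the untransformed scale, or dropped, and make the SAP match.
- **Protocol 5.8.2.1 and 5.8.2.2:** reconcile the nadir wording with the chosen direction, leaving every dose as it is.
- **SAP:** in 4.2, replace Neopterin-Cmin with the maximum-increase variable modelled in 7.5. Rename the dec, max symbols throughout.

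The cost is wording in the protocol and the SAP. Sampling, sample size and doses do not change. If the ANCOVA and intervals are kept, the SAP also needs a short model statement.
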